Table 2. Roles and Responsibilities.....	19
14. Documentation Checklist.....	19
15. Reference List	19
16. Appendices.....	19

1. Study Synopsis

Study Information	
Study Type	Retrospective chart review
Study Device(s)	Profound Matrix System is a platform of 3 applicators: Sublime, Sublative RF and Matrix Pro. The Matrix Pro applicator, a new short pulse RF micro-needling device that treats with an array of RF micro-needles penetrating the skin, will be assessed in this retrospective analysis.
Indication(s)	Wrinkles
Treatment area(s)	Full face
Overall Study Objective	Evaluate the safety and efficacy of the Profound Matrix System with the Matrix Pro applicator for treatment of wrinkles
Target Enrollment	This is a retrospective chart review evaluating all subjects enrolled into the FUFT2002 source study meeting inclusion criteria and none of the exclusion criteria of this study protocol for retrospective analysis.
Study duration	N/A – this is a retrospective chart review
Study Site(s)	In the source study from which data for the current retrospective study will be extracted, subject enrollment occurred at up to five (5) clinical sites.
Study Design	This study is a retrospective analysis of de-identified subject data collected during implementation of the clinical study, “Functional Usability and Feasibility Testing of the Profound Matrix™ System (FUFT2002)” (source study). The FUFT2002 clinical study was a multi-site prospective clinical trial. The current retrospective study will analysis data extracted from the FUFT2002 database according to prespecified study selection criteria.
List of Measures	
 • Before and after photograph assessment • Subject satisfaction questionnaire • Pain/ discomfort during treatment using Numerical Rating Scale (NRS) • Adverse events evaluation
Primary Efficacy Endpoint(s)	The Primary Efficacy Endpoint is pre-defined as the percentage correct before and after photograph determinations made by blinded evaluators based on perception of facial wrinkles.

[figure not shown]

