Efficacy Variables:	
 Subject Global Aesthetic Improvement Scale (GAIS): A 5-point scale assessing the subject's satisfaction with any perceived overall improvement in their facial appearance following the treatments with the study device.  
 Numerical Rating Scale (NRS): A horizontal line scale from 0 to 10, with 0 equaling no pain and 10 equaling the worst possible pain. The subject is asked to mark the point on the scale that best represents their current pain level.  
 Post-treatment Severity Scale: A 0 to 3 categorical scale presented below. 
Safety Variables:	
Assessment of safety of Matrix Pro treatment(s) for wrinkle reduction will be through:
 
 Evaluation of the number, severity, and type of any device-related adverse event that occurs throughout the course of the study from baseline through to the 3-month follow-up evaluation visit. Subject assessment of treatment discomfort/pain recorded immediately post-treatment via the 11-point Numerical Rating Scale (NRS). Investigator assessment of local skin responses recorded immediately post-treatment, evaluated by type and severity.

	Name: MXP23001 Statistical Analysis Plan	
Number: 10-040-02025	Effective Date: See Agile	Revision: A

HYPOTHESIS

Table 5

Statistical Criteria for Hypothesis	
Efficacy Variables:	
Primary Efficacy variable is according to pre-determined responder rate criteria as follows:
 
Null Hypotheses:
 
 • The proportion of individual subject successes for primary endpoint, i.e., the proportion of individual subjects for whom at least 2 of the 3 blinded evaluators correctly identifies the Before-After photo order, will be less than 70%. 
Alternative Hypothesis:
 
 • The proportion of individual subject successes for primary endpoint i.e., the proportion of individual subjects for whom at least 2 of the 3 blinded evaluators correctly identifies the Before-After photo order, will be 70% or greater. 
Statistical hypotheses for secondary variables are not applicable as secondary variables will be evaluated descriptively only.
 
 NA, Explain rationale: N/A

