Safety Variables:	
 NA, Explain rationale:
 
Statistical hypotheses for safety variables are not applicable as formal safety evaluation is not required for this non-significant risk (NSR) retrospective study. As such, statistical significance evaluation of outcome is limited to the primary efficacy variable only, as explained above.

SAMPLE SIZE

Calculating Sample Size

Table 6

Sample Size Justification	
Clinical Background:	
The parameters used for sample size calculation were determined from that employed in prior pivotal clinical trials whose outcome data was used to successfully support an FDA 510(k) clearance for a comparable indication to that being evaluated in this study.

Expected Outcomes:	
As this is a retrospective, single arm study, minimally clinically meaningful difference between treatment groups is not applicable.
 
Expected outcome is that within the single arm active treatment group, the pre-determined primary success criteria of at least 2 of the 3 blinded evaluators correctly identifying the Before-After photo order for a minimum of 70% of subjects, will be met.

Estimated Retention	
N/A – This is a retrospective clinical study

Effect Size	
 N/A, Explain rationale:
 
There is no comparator arm.

Significance Level and Power Justification:	
Significance Level: $\alpha = 0.05$
 
Power: 80%
 
Type of t-test: Responder Rate Analysis: percent of successes.
 
 N/A, Explain rationale: N/A

	Name: MXP23001 Statistical Analysis Plan	
Number: 10-040-02025	Effective Date: See Agile	Revision: A

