Sample Size Calculation and Justification	
Employing these parameters, the minimum pre-determined sample size to provide sufficient power for a statistical comparison of the proportion of treatment responders (P) versus a reasonable cutoff (P0) is based on a power calculation utilizing the (one proportion) binomial exact test and based on the following assumptions.
 

 
Therefore, a sample size of 24 study subjects is determined to be sufficient to provide appropriate sample population for statistical analysis such that the results of this retrospective study can be considered statistically and clinically meaningful and generalizable to the broader intended population.
 
 N/A, Explain rationale: N/A

Target Number of Subjects per Site	A sample size of 24 study subjects has been determined sufficient to provide an appropriate sample population for statistical analysis and generalizability of results.

GENERAL ANALYSIS CONSIDERATIONS

Timing of Analyses

- The final analysis for primary efficacy will be performed after all qualified subjects from the source study have been identified per the retrospective study inclusion and exclusion criteria and enrolled in the retrospective study, after the final data entry has been entered into the current study database, and after each of the three independent blinded evaluators have completed their Before-After blinded photographic assessments.
- The final analysis will be performed on data recorded in the electronic Excel database, having been documented as meeting the cleaning and approval requirements of SOP 10-030-01617 (Global Clinical Data Management Procedure) and after the finalization and approval of this SAP document.

Analysis Populations

Table 7

Study Design and Plan	
Full Analysis Population/ Intention to Treat Population (or Modified Intention to Treat Population):	The Full Analysis Population in this retrospective study will be the per protocol population including all enrolled subjects who had valid recorded baseline and study endpoint outcomes recorded during the source study, including evaluable photographs at both assessments. The Full Analysis Per Protocol population analysis will be the primary and only analysis population in this retrospective study.

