Any additional protocol deviations that occurred in the source study that are relevant to the current study will be listed and explored as applicable. There is no criteria for reporting of any protocol deviation that may potentially cause harm to a subject to the IRB as the source study is complete and any such reporting requirements have already been satisfied.

Demographic and Baseline Variables

The demographic or baseline variables that will be recorded in this clinical study are age, gender, race/ethnicity, and Fitzpatrick Skin Type (I through VI).

Depending on the final enrollment sample, age may be transformed into category, within the inclusion range of 18-75 years.

Demographic/baseline variables will also be summarized by test site.

Concurrent Illnesses and Medical Conditions

Subject medical history and concomitant medication use will not be specifically evaluated in this retrospective study. It is a condition of eligibility in this retrospective study that qualified subjects met the eligibility criteria under FUFT2002 and were enrolled into FUFT2002 study at which time any medical history and concomitant medication use that would be pertinent inclusion/exclusion criteria for the current retrospective study would have been satisfied. Given that the current study is retrospective, medical history and concomitant medication use will not be tracked throughout the course of the study, and as such, no coding system needs to be implemented.

Treatment Compliance

As this study is a retrospective study, assessment of treatment compliance is not applicable.

	Name: MXP23001 Statistical Analysis Plan	
Number: 10-040-02025	Effective Date: See Agile	Revision: A

EFFICACY ANALYSES

The primary efficacy variable will be listed by subject. Primary data will be summarized across the pooled subject group. N, Mean, Standard Deviation, Minimum and Maximum will summarize continuous efficacy variables, whereas number and percent will summarize categorical efficacy variables, including responder rate variables.

Responder rate variables will be assessed against a predetermined criterion.

Categorical efficacy measures will be evaluated descriptively within evaluations and for change across evaluations.

Primary Efficacy Analysis

Primary Efficacy Endpoint is pre-defined as the percentage correct before and after treatment photograph determinations made by blinded evaluators based on perception of facial wrinkles.

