There will be 3 independent blinded evaluators partaking in the study. Each will receive the set of subject photographs in de-identified coded randomized order (randomized for before and after treatment presentation order with respect to each subject photograph set, and with respect to order of subject set presentation). The blinded evaluators will be required to determine within each presented photographic set which of the images is the 'After' image (3-months post-treatment administration) based on his or her perception of the presentation of facial wrinkles. Each blinded evaluator will perform this task independently of the other. A minimum of 2 out of the 3 blinded evaluators correctly determining Before-After assignment for an individual subject's photograph set will indicate success for that individual subject with respect to positive treatment response. Seventy percent (70%) overall individual responder rate will be positive for study success.

Secondary Efficacy Analyses

Secondary measures efficacy analysis will be conducted descriptively only through summary statistics such as means, standard deviations, and ranges for qualitative data, percentages per category, and in tabular and/or graphical format, as applicable to the data type (qualitative or quantitative, continuous, or categorical, etc.).

Subgroup analysis of the primary efficacy endpoint may be performed for the variables of age, gender, and Fitzpatrick Skin Type.

Secondary Analyses of Primary Efficacy Endpoint

Secondary analysis of the primary efficacy endpoint is not applicable as the per protocol population is the only population being evaluated in this retrospective study.

Exploratory Efficacy Analyses

Evaluation of exploratory endpoints may occur informally.

SAFETY ANALYSES

Each of the following safety outcome variables as recorded during the source study for subjects enrolled in the current study will be reported, evaluated, and discussed numerically and descriptively, as applicable:

[figure not shown]
- The incidence, severity, and type of any device-related adverse event that occurred throughout the course of the study from baseline through to the 3-month follow-up evaluation visit.
- Subject reports of treatment discomfort/pain recorded immediately post-treatment using the 11-point Numerical Rating Scale (NRS).
- Investigator assessment of local skin responses recorded immediately post-treatment, evaluated by type and severity.

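### The 70% success rule applies to whatever number of subjects qualifies, so it is tied neither to the stated 5% level nor to the 24 subjects behind the stated 80% power

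*SAP*

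**What the plan says.** **Success rule.** SAP, Primary Efficacy Analysis: "Seventy percent (70%) overall individual responder rate will be positive for study success". The same 70% rule stands in SAP Table 2, the Protocol synopsis and Protocol section 11. The opening of the SAP's Efficacy Analyses section adds only this: "Responder rate variables will be assessed against a predetermined criterion". No test is named there.

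**Hypotheses.** In SAP Table 5 the null is that the proportion of subjects for whom at least two of three evaluators "correctly identifies the Before-After photo order, will be less than 70"%. The alternative is that it "will be 70% or greater".

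**Sample size.** SAP Table 6 gives a significance level of 0.05 and 80% power. It presents 24 as "the minimum pre-determined sample size to provide sufficient power for a statistical comparison of the proportion of treatment responders", using a one-proportion exact binomial test of P against a cutoff P0. The values of P0 and P are blacked out. Retention is marked not applicable, so there is no allowance for loss.

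**How N arises.** The Protocol synopsis (Target Enrollment) describes a review "evaluating all subjects enrolled into the FUFT2002 source study meeting inclusion criteria and none of the exclusion criteria". Protocol section 10 says the source study is complete. Protocol section 5 lists five exclusions, among them photographs that cannot be compared. Under Timing of Analyses, the SAP starts the final analysis once all qualified subjects have been identified and read, with no minimum count. No visible text says what follows if fewer than 24 qualify.

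**The concern.** A level of 5% and a power of 80% belong to a particular N and a particular count of responders. Here N is whatever survives selection from a closed study, and a shortfall cannot be made up by further enrolment. The success rule is a percentage, and its error rate moves with N. Success could therefore be declared on, say, 7 of 10 or 14 of 20 subjects, with the report still carrying a level and power worked out for 24.

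The study exists to support a single pass/fail claim, and Table 6 calls the result statistically meaningful on the strength of that 24. The number who qualify can be counted before any photograph is read, so the matter can be settled without knowledge of the outcome.

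**Working it through.** **Inputs**
- Pass mark under the plan: c = 0.70 × N, rounded up (SAP, Primary Efficacy Analysis).
- Level 0.05, power 80%, N = 24 (SAP Table 6). Sidedness is not stated. The hypotheses are directional, so one-sided 0.05 is used.
- P0: blacked out. Assumed to be 0.5. If each evaluator guesses, the chance that at least two of three are right is 3 × 0.5² × 0.5 + 0.5³ = 0.375 + 0.125 = 0.5. Values of 0.45 and 0.55 are shown as a range.
- Stated null boundary: 0.70 (SAP Table 5).

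**Formula.** The chance of passing at true responder rate p is P(X ≥ c), with X binomial (N, p), computed exactly.

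**The plan's own figure.** Without P0 and P, 24 can be neither reproduced nor refuted. It is compatible with several pairs. One is P0 = 0.55 and P = 0.80, one-sided: pass mark 18/24, power 81.1%. Another is P0 = 0.50 and P about 0.76, one-sided: pass mark 17/24, power about 80%.

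**The 70% rule at different N**

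| N | Pass mark | Passes if true rate 0.50 | Passes if true rate 0.70 |
|---|---|---|---|
| 24 | 17 | 3.2% | 56.5% |
| 23 | 17 | 1.7% | 44.0% |
| 22 | 16 | 2.6% | 49.4% |
| 21 | 15 | 3.9% | 55.1% |
| 20 | 14 | 5.8% | 60.8% |
| 19 | 14 | 3.2% | 47.4% |
| 18 | 13 | 4.8% | 53.4% |
| 17 | 12 | 7.2% | 59.7% |
| 16 | 12 | 3.8% | 45.0% |
| 15 | 11 | 5.9% | 51.5% |
| 14 | 10 | 9.0% | 58.4% |
| 13 | 10 | 4.6% | 42.1% |
| 12 | 9 | 7.3% | 49.3% |
| 10 | 7 | 17.2% | 65.0% |

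Against 0.50, the rule exceeds 5% at N = 3 to 12, 14, 15, 17 and 20. It stays below 5% at 13, 16, 18, 19 and 21 to 24. The sawtooth comes from rounding 0.70 × N up to a whole subject.

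**Range for P0.** At 0.45 the rule passes 1.0% of the time at N = 24, 2.1% at 20, 4.3% at 14 and 10.2% at 10. At 0.55 the figures are 8.6%, 13.0%, 16.7% and 26.6%.

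**Against the stated null of 70%.** The right-hand column lies between 42% and 65% throughout and shows no systematic worsening as N falls. An exact one-sided 5% test against 0.70 would need 21/24 (level 4.2%).

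**Pass marks that hold 5% for P0 = 0.50**

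| N | 70% mark | Exact mark | Level at exact mark | Power at true 0.80: 70% mark | Power at true 0.80: exact mark |
|---|---|---|---|---|---|
| 20 | 14 | 15 | 2.1% | 91.3% | 80.4% |
| 17 | 12 | 13 | 2.4% | 89.4% | 75.8% |
| 14 | 10 | 11 | 2.9% | 87.0% | 69.8% |
| 10 | 7 | 9 | 1.1% | 87.9% | 37.6% |

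At N = 21 to 24 the 70% mark already meets the exact test against 0.50, so nothing changes there. At N = 24 the power is 76.6% at a true rate of 0.75 and 91.1% at 0.80.

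**The case against.** **The count of 24 is already called a minimum.** It is, but as a planning figure. Neither the success rule nor the analysis trigger uses it.

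**The exact binomial test would hold the level at any N.** This is the strongest point. If that test were applied at the achieved N, the level would stay at or below 5%, and only power would depend on 24. But the test appears only in the sample-size justification. The Efficacy Analyses section does not make it a condition of success.

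**The trigger is unknown.** This stands. The documents do not give the number qualifying, and nothing shows that it will fall below 24.

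**A reader might infer that any N below 24 pushes the false-success rate above 5%.** The figures do not support that. Between 18 and 23 only N = 20 exceeds 5% against 0.50, and 22 and 23 do better than 24.

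**A reader might also infer that 24 subjects secure the 5% level, so that a minimum N would be the cure.** The documents do not support that either. Against the null in SAP Table 5 the rule passes 56.5% of the time at N = 24. A flat bar below 24 would also refuse a result such as 23 of 23, which passes any of the exact tests considered here.

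**The Table 6 row for subjects per site repeats the total** ("A sample size of 24 study subjects has been determined sufficient to provide an appropriate sample population for statistical analysis and generalizability of results"). With up to five sites the label is confusing, but it is clerical and does not affect the success rule.

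**Conclusion.** The concern holds in a limited form. As written, the rule fixes neither the error rate nor the power, because both depend on an N that the plan leaves open and on a test that the rule does not invoke. With P0 assumed to be 0.5, the excess over 5% is small at N = 20 (5.8%), larger at 14 (9.0%) and serious at 10 (17.2%), and it is absent at several other sizes below 24. If P0 is nearer 0.45, the excess disappears at 14, 17 and 20. If it is nearer 0.55, the rule already exceeds 5% at 24. The lack of a link to the stated 80% power applies at every N other than 24. The gap between the rule and the stated 70% null is larger, and a minimum N alone would not close it.

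**What to change.** In SAP Primary Efficacy Analysis and Protocol section 11:

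1. Lock the list of qualifying subjects before the first photograph read.
2. Write the actual N into the SAP.
3. State an integer pass mark at that N: the larger of 70% of N rounded up and the smallest count at which the one-sided exact binomial test against the plan's stated P0 gives 0.05 or less. For P0 = 0.5 this is 15/20, 13/17, 11/14 or 9/10. The SAP should say how this P0 relates to the 70% null in Table 5, since an exact test against 0.70 would need 21/24.
4. Replace the stated 80% with the power at the actual N and pass mark.
5. Report the responder rate with an exact confidence interval.
6. If N is below 24, say that the planned minimum was not reached, without barring a claim that meets the exact pass mark.

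The Table 6 row can be relabelled as a total at the same time.

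The cost is SAP and protocol wording and one database count. For P0 = 0.5 the pass mark does not change at N = 21 to 24. It rises by one responder at 14, 17 and 20 and by two at 10, and the stated power may be less favourable than 80%.

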There will be 3 independent blinded evaluators partaking in the study. Each will receive the set of subject photographs in de-identified coded randomized order (randomized for before and after treatment presentation order with respect to each subject photograph set, and with respect to order of subject set presentation). The blinded evaluators will be required to determine within each presented photographic set which of the images is the 'Before' image (prior to treatment initiation) and which is the 'After' image (3-months post-treatment administration) based on his or her perception of the presentation of facial wrinkles. Each blinded evaluator will perform this task independently of the other. A

minimum of 2 out of the 3 blinded evaluators correctly determining Before-After assignment for an individual subject's photograph set will indicate success for that individual subject with respect to positive treatment response. 70% overall individual responder rate will be positive for study success.

The rationale for selection of a minimum responder rate criterion of 70% (based on a 2 out of 3 blinded evaluator concordance) is based on the minimum requirement established by the United States Food and Drug Administration (U.S. FDA) to which Candela Corporation has been upheld and successfully employed previously to attain FDA market clearance for similar devices and indications.

[figure not shown]
Employing these parameters, the minimum pre-determined sample size to provide sufficient power for a statistical comparison of the proportion of treatment responders (P) versus a reasonable cutoff (P0) is based on a power calculation utilizing the (one proportion) binomial exact test and based on the following assumptions.

[figure not shown]

Therefore, a sample size of 24 study subjects is determined to be sufficient to provide appropriate sample population for statistical analysis such that the results of this retrospective study can be considered statistically and clinically meaningful and generalizable to the broader intended population.

General Overview of Statistical Plan

Efficacy analysis will be performed for both the primary modified intent-to-treat (mITT) and the secondary per protocol (PP) populations. Safety will be evaluated for the safety population. Each is defined below.

Handling Missing Data

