Per Protocol Population	The per protocol (PP) population as explained above will be the primary and only analysis population in this retrospective study.

Covariates and Subgroups

Multi-center Studies

- Individual center results will be pooled together to perform the final efficacy analysis.

	Name: MXP23001 Statistical Analysis Plan	
Number: 10-040-02025	Effective Date: See Agile	Revision: A

- The justification for combining of study data across test sites is based on the clinical assessment provided by Meinert (1): the clinical (source) study was conducted under a common protocol for each investigational site, the study sites were monitored for protocol compliance, and the same data gathering instruments and methods were used at every site.
- Justification of the plausibility of combining of study data across test sites will be conducted through Fischer's Exact Test to evaluate for homogeneity of Responder Rates (study Primary Efficacy Outcome assessment) between test sites.

This study has not been explicitly designed with enough power to detect center effects. Therefore, treatment-by-test site interactions will be analyzed descriptively only through tables and charts, using N, mean, standard deviation, and minimum-maximum values. **Missing Data**

As by virtue of the study selection criteria, qualifying subjects will have had valid required measures recorded at baseline and endpoint assessments for the current study, including evaluable digital photographs, handling of missing data is not applicable.

Interim Analyses and Data Monitoring (as applicable)

N/A

Table 8

Interim Analysis Plan	
Purpose of Interim Analysis	 N/A, Explain rationale: There is no uncertainty as to the study design, treatment parameters, outcome variables, study endpoints, or endpoint analyses.
Planned Schedule of Interim Analyses	 N/A, Explain rationale: No interim analysis is planned for this study.
Scope of Adaptations	 N/A, Explain rationale: No interim analysis is planned for this study.
Stopping Rules	 N/A, Explain rationale: No interim analysis is planned for this study.
Analysis Methods to Minimize Bias	 N/A, Explain rationale: No interim analysis is planned for this study.

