Adjustment of Confidence Intervals and p-values	 N/A, Explain rationale: No interim analysis is planned for this study.
Interim Analysis for Sample Size Adjustment	 N/A, Explain rationale: No interim analysis is planned for this study.
Practical Measures to Minimize Bias	 N/A, Explain rationale: No interim analysis is planned for this study.
Documentation of Interim Analyses	 N/A, Explain rationale: No interim analysis is planned for this study.

SUMMARY OF STUDY DATA

- All continuous variables will be summarized in tables using the following descriptive statistics: n, mean, standard deviation, maximum and minimum.

	Name: MXP23001 Statistical Analysis Plan	
Number: 10-040-02025	Effective Date: See Agile	Revision: A

- All categorical measures will be summarized in tables and/or charts as frequencies and/or percentages of observed levels.
- Summary tables will be structured with a column for the treatment and rows for the variables.
- Primary efficacy outcome data will additionally be listed by subject, and sorted by site, and when appropriate by visit within subject.

Subject Disposition

The following variables from the CRF will be used to establish subject disposition with respect to those selected from the source study per the current retrospective study selection criteria:

- Number received two or three study treatments and completed 1-month and 3-month follow-ups = Per Protocol population

Determination of population membership and population size per treatment group is not applicable as this study is a single arm design with no sham or control arm.

Derived Variables

The primary endpoint of blinded evaluator before/after photo determination will be derived from the photographs that are source documents recorded at the respective evaluation timepoints during the study from which the current retrospective study data will be drawn.

Protocol Deviations

There are no significant protocol deviations in the current retrospective study that could impact the study primary outcomes analysis. With respect to the source study, given that the subject selection criteria will result in a per protocol analysis population only for the current study data, there will be no major protocol deviations that could impact that study's primary outcomes analysis.

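### The safety tables cover only subjects selected for a photograph endpoint; the protocol's safety population is absent from the SAP, and no visible planned table counts the treated subjects left out

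*SAP*

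**What the plan says.** **Protocol.** Section 11 (General Overview of Statistical Plan) gives efficacy two populations: "Efficacy analysis will be performed for both the primary modified intent-to-treat (mITT) and the secondary per protocol (PP) populations". It gives safety its own: "Safety will be evaluated for the safety population". It announces definitions, but these are not in the available text.

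Section 1 (Target Enrollment) limits the study to FUFT2002 subjects who pass this study's selection. Section 5 excludes for sun exposure, other aesthetic procedures, violation of treatment instructions, photographs that cannot be compared, and deviations or visit changes that threaten the review. Section 10 (Data Collection Methodology) limits extraction to subjects who qualify. Section 8 extracts adverse events only for subjects evaluated in this study.

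**SAP.** Table 7 states: "The Full Analysis Per Protocol population analysis will be the primary and only analysis population in this retrospective study". Its per-protocol row repeats this, and Secondary Analyses of Primary Efficacy Endpoint says much the same. No safety population appears. Safety Analyses sets the scope: "Each of the following safety outcome variables as recorded during the source study for subjects enrolled in the current study will be reported". Protocol Deviations describes the result of selection: "given that the subject selection criteria will result in a per protocol analysis population only for the current study data". Missing Data adds that "qualifying subjects will have had valid required measures recorded at baseline and endpoint assessments for the current study, including evaluable digital photographs". Subject Disposition shows one item: "Number received two or three study treatments and completed 1-month and 3-month follow-ups = Per Protocol population".

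**The concern.** Safety is half of the stated objective. For descriptive safety tables the natural denominator is everyone who was treated. Here it is filtered by criteria written for a before-and-after photograph comparison. A change of chin position or expression between photographs has no bearing on whether a treated subject's adverse event should count.

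A completion condition would matter more. Protocol Section 6 allowed up to three treatment visits, and Section 5 (Study Participant Retention Plan) let source-study subjects leave at any time. Someone who stopped after one session because of pain or a skin reaction is the subject a safety table most needs. The documents do not say that there was such a subject. The concern is that the visible plan would not show it if there were.

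**Working it through.** **1. Who can enter the safety tables**

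| Step | Source | Effect |
|---|---|---|
| Selection | Protocol Sections 1 and 5 | Only subjects who meet this study's criteria |
| Extraction | Protocol Sections 8 and 10 | Data, adverse events included, only for those subjects |
| Safety scope | SAP, Safety Analyses | Subjects enrolled in the current study |
| Result of selection | SAP, Protocol Deviations | PP subjects only |
| PP membership | SAP Table 7; Subject Disposition | Valid baseline and endpoint outcomes with evaluable photographs; two or three treatments and both follow-ups |

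On the SAP's own account, enrolled and PP are the same set. The SAP's Adverse Events section includes all adverse events, which widens the events counted but not the subjects.

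**2. Two levels of certainty**

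- *Established by visible criteria:* treated subjects removed for photograph comparability, sun exposure, other procedures, treatment-instruction violations or qualifying deviations are outside the tables.
- *Apparent only:* single-session or missed-visit subjects. Their loss follows from joining the Protocol Deviations and Subject Disposition statements. No visible exclusion criterion names them, and the inclusion criteria are not in the available text.

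**3. Is anyone left out counted?** The lead-in to SAP Subject Disposition covers selected subjects only. The missing-data table in Protocol Section 11 can reach only extracted subjects, and the SAP calls missing-data handling not applicable. SAP Protocol Deviations lists source-study deviations relevant to this study; that is not a count of unselected subjects. So no visible planned table counts them.

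**4. What could be at stake numerically**

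The plan states no figure to reproduce on this point. The planned N of 24 (Protocol Section 11; SAP Table 6) is used only as a denominator and is not disputed. Everything else is assumed: m treated-but-unselected subjects, event rate p in the 24 and q in the m.

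All-treated rate = (24p + mq)/(24 + m) = p + [m/(24 + m)] × (q − p)

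| m | Weight m/(24 + m) | q = p | q − p = +10 points | q − p = +20 points | p = 2/24 = 8.3%, q = 0 |
|---|---|---|---|---|---|
| 0 | 0/24 = 0% | 0 | 0 | 0 | 0 |
| 4 | 4/28 = 14.3% | 0 | +1.4 | +2.9 | −1.2 |
| 8 | 8/32 = 25.0% | 0 | +2.5 | +5.0 | −2.1 |
| 12 | 12/36 = 33.3% | 0 | +3.3 | +6.7 | −2.8 |

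The last four columns give the shift in percentage points from the PP rate to the all-treated rate. For scale, zero events in 24 leaves an exact one-sided 95% upper limit of 1 − 0.05^(1/24) = 11.7%. The illustrated shifts are smaller than that. But the 11.7% can be read off the reported denominator, whereas m and q cannot be recovered from any visible table.

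**The case against.** The strongest reply is that the narrow scope is the design. The protocol itself confines the study and its extraction to qualifying subjects, and its definition of the safety population is not visible and may be just as narrow. This stands against one tempting inference: that the SAP drops subjects whom the protocol would have kept. The documents do not show that. The mismatch between the two documents remains, because a statistician following the SAP has no safety population to run.

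Second, Safety Analyses says enrolled, not PP. Table 7 reads as if PP were a subset of enrolled, and the disposition count would be redundant if every selected subject were PP. This also has force. It is why the loss of single-session or missed-visit subjects is put here as apparent and not as a stated rule.

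Third, the disposition list may contain items that are not visible. A reader therefore cannot conclude that the full plan offers no check, only that none is visible.

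Fourth, the statement that the "results of this retrospective study can be considered statistically and clinically meaningful and generalizable to the broader intended population" closes the sample-size justification for the primary efficacy endpoint. A reader might take it as a claim that the safety rates generalise, but it makes no separate safety claim.

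Fifth, SAP Table 5 says formal safety evaluation is not required. That explains why no safety hypothesis is tested. It does not explain why descriptive tables cover selected subjects only.

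**Conclusion.** The point holds as a cheap and worthwhile correction. The documents disagree on the safety population. As written, the adverse-event, pain and skin-response rates are filtered by criteria that serve the photograph endpoint, and no visible table counts the treated subjects left out.

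The size cannot be determined. The number of unselected subjects and their events are not given, so any bias may be upward, downward or nil; the table above is illustration only. A reader might infer that the reported rates will be too favourable, or that events went unreported. Neither is supported: nothing shows that unselected subjects fared worse, and Protocol Section 8 says adverse-event reporting was in effect under FUFT2002. The limit is on this study's tables. The efficacy conclusion is unaffected.

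The conclusion rests on the visible text, chiefly the SAP's statement that selection leaves a PP population only. A visible definition of the safety population, or further disposition items, could narrow it.

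**What to change.** 1. Reconcile Protocol Section 11 with SAP Table 7, and state in the SAP whether enrolled equals PP for safety.
2. Add a source-to-selected table: FUFT2002 subjects treated with Matrix Pro, selected and excluded, with reasons and any adverse events among the excluded.
3. Preferably, run the adverse-event, NRS and skin-response tables on all FUFT2002 subjects with at least one full-face Matrix Pro treatment within the study's indication, with PP as a second column. The indication and area need stating because Protocol Section 4 describes sites with experience in several uses. Amend the extraction limit in Protocol Sections 8 and 10 for safety fields only, after checking that the exemption and privacy waiver in Section 7 cover it, and say that this widens the Section 1 scope.
4. If the sponsor keeps the narrower scope, the table in item 2 is the minimum, and the safety tables should be labelled as covering selected subjects only. The selection query already goes through the FUFT2002 data, so counts and reasons should be close to hand. The adverse-event column reaches beyond the current extraction limit and needs the same coverage check.

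The cost is a short protocol and SAP amendment, a wider query of an existing database, and reported rates that may be less favourable. No new data are collected.
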